7.3 Analysis of Safety Endpoints

For analysis of safety endpoints, summary tables and/or listings will be provided for all adverse events by event category. Adverse events will also be summarized by relationship to the study device, implant procedure, by seriousness, severity and by outcome. Adverse events leading to discontinuation from the study will be tabulated. Except where indicated, a subject reporting the same adverse event more than once will be counted once when calculating the number and percentage of subjects with that particular event. Except where indicated, if a subject reports the same adverse event more than once, the strongest relationship to the procedure and/or device recorded for the event will be presented.

Adverse events that occurred in screen failure subjects will be presented separately.

7.4 General Statistical Methods

Only descriptive statistics will be used, including mean, standard deviation, and range.

7.4.1 Surgery and Supporting Procedures

Detailed information regarding the surgical procedure will be presented in listings. This will include information on crestal bone measurements, bone quality, evaluation of primary stability, and soft tissue procedures.

Details regarding other supportive procedures in the study will be presented in listings, including suture removal, second stage surgery, soft tissue procedures, impressions, temporary prosthesis placement, and definitive prosthesis placement.

7.4.2 Other Data Summaries

Concomitant medications will be presented in listings and also summarized by drug category. Protocol deviations will be summarized by deviation type and study center.

7.4.3 Subject Disposition

A detailed description of subject disposition will be provided using a CONSORT diagram and summaries of subjects falling in various subgroups of interest, such as enrolled but did not receive study treatment and early withdrawals. All enrolled subjects entered in the study will be accounted for in the summary.

7.4.4 Missing Data

Every effort will be made to minimize the amount of missing data. If a subject drops out of the study prior to completing their primary endpoint assessment, every effort will be made to measure their primary endpoint immediately prior to discontinuation if possible. No missing data will be imputed.

8 Data Management

The general data management procedures are described below, details can be found in the Data Management Plan. Required clinical data for this study will be collected and recorded in the clinical database using an electronic case report form for all study subjects from whom informed consent is obtained. Research Center numbers and subject numbers will be used to track subject information throughout the registry. The Principal Investigator or authorized designee is responsible for the timely completion and electronic signature of all electronic case report forms. The information entered into the database will be checked systematically by the data management for inconsistent, illogical and/or missing data using electronic and manual validation checks defined

in the Data Validation Plan. If validation of data leads to discrepancies, data management will generate electronic queries. The timely resolution of the queries is under the responsibility of the monitor and the investigators at the Research Center. The query process is an ongoing process starting with the first data entered into the database. The electronic clinical data system used for this study has a security system that prevents unauthorized access to the data and any deletion of data (audit and edit trail).

9 Study Management

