GBR	Guided Bone Regeneration
GCP	Good Clinical Practice
GTR	Guided Tissue Regeneration
HDD	Horizontal Dimension of Defect
IFU	Instructions for Use
IRB	Institutional Review Board
ISO	International Organization for Standardization
ISQ	Implant Stability Quotient
ITT	Intention To Treat population
mITT	Modified Intention to Treat
mGI	Modified Gingival Index
mm	Millimeter
mSBI	modified Sulcus Bleeding Index

Ncm	Newton Centimeter
PII	Plaque Index
PP	Per Protocol population
PPD	Probing Pocket Depth
PSP	Photostimulable Phosphor
RFA	Resonance Frequency Analysis
SADE	Serious Adverse Device Effect
SAE	Serious Adverse Event
SAF	Safety Population
TN-SM	Tetranite [®] - Stabilization Material
USADE	Unanticipated Serious Adverse Device Effect
VAS	Visual Analog Scale

Synopsis

Oynopsis	
Study Title:	Immediate Placement and Stabilization of Dental Implants with Tetranite [®] Stabilization Material in Mandibular and Maxillary Tooth Extraction Sites that Fail to Provide Adequate Primary Stability – A Pilot Study
Study Protocol Number:	DVAL18041
Study Registration:	This protocol will be registered at www.clinicaltrials.gov before enrollment begins.
Aim:	The aim of this Pilot Study is to demonstrate the safety and efficacy of the use of Tetranite-Stabilization Material (TN-SM) to allow clinical study of the TN-SM device in a greater number of patients.
Primary Endpoint:	 The primary endpoint is a composite measure of implant success (after criteria of Buser, et. al.¹) at six-month post-functional loading consisting of: Presence of the implant at its site of implantation; and,
	Absence of a recurrent peri-implant infection with suppuration; and,
	Absence of mobility, defined as:
	 Lack of implant rotation subjected to 20 Ncm of clockwise torque applied 15 minutes after implant placement; and.
	 Lack of implant rotation subjected to 35 Ncm of clockwise torque applied 13 weeks after implant placement; and,
	 No construct mobility upon palpation at 6 months post- functional loading; and,
	 Absence of encapsulation defined as continuous radiolucency around the implant in a periapical radiograph.
Secondary Endpoints:	Incidence, severity and duration of device-related adverse events throughout the 12-month post-functional loading term;
	Implant success (after criteria of Buser, et. al. ¹ , see primary endpoint) after implants are stabilized with the TN-SM device throughout the 12-month post-functional loading term;

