2.1 Primary Endpoint (Composite)

The **primary endpoint** is implant success through six-months of post-functional loading. The implant success criteria will be collected on a per patient level and are a composite of implant survival, health and efficacy measures, based after criteria of Buser, et. al. ¹, including:

- Presence of the implant at its site of implantation; and,
- Absence of a recurrent peri-implant infection with suppuration; and,
- Absence of mobility, which will be assessed at multiple timepoints. Specifically,
 - Immediate stabilization (implant placement, Visit 3) is assessed by applying a torque of 20 Ncm applied directly to the implant 15 minutes after implantation.
 - Short-term stabilization (implant uncovering, Visit 5) is assessed by applying a torque of 35 Ncm 13 weeks after implant insertion.
 - Continued stabilization is assessed at 6-months post-functional loading (Primary Follow-up, Visit 9) by applying manual palpation.
- Absence of encapsulation determined by a continuous radiolucency around the implant assessed via periapical image.

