3.11 Study Assessments

3.11.1 Implant Success

Implant success will be assessed at post-functional loading follow-ups. A successful implant will meet all of the following criteria according to Buser et al.¹; including,

- Presence of the implant at its site of implantation;
- Absence of a recurrent peri-implant infection with suppuration;
- Absence of mobility, which will be assessed at several timepoints. Specifically,
 - Immediate stabilization (implant placement, Visit 3) is assessed by applying a torque of 20 Ncm applied directly to the implant 15 minutes after implantation.
 - Short-term stabilization (implant uncovering, Visit 5) is assessed by applying a torque of 35 Ncm 13 weeks after implant insertion.
 - Long term stabilization is assessed every 3 months post-functional loading until 24months post-functional loading by manual palpation.
- Absence of encapsulation determined by a continuous radiolucency around the implant recorded in a periapical image.

Any dental implant showing excessive bone loss, radiolucency, or infection shall be treated in the manner best suited to the well-being of the subject, including treatment to save the dental implant. Continuous radiolucency, implant loss, recurrent peri-implant infection with suppuration, or implant mobility shall be considered a failure for the purposes of the study.

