5.1 Schedule of Procedures and Assessments

The schedule of administrative, treatment and evaluation visits will follow the matrix detailed in Table 1. The timing of the scheduled events listed in the table will be acceptable if it is within the tolerances listed. Except for the First Surgical Visit, i.e., the extraction, test device and implant placement visit, it is permissible for portions of the procedures to be completed on separate visits provided they are within the allowable schedule windows. A record of procedure and evaluation dates will be maintained.

Table 1: Schedule of Procedures and Assessments

Visit # Visit Name Visit Window	Visit #	Visit Name	Visit Window
---------------------------------	---------	------------	--------------

Visit 1	Screening	
Visit 2	Qualifying Examination	
Visit 3	First Surgical	< 45 days from screening
Visit 4	Post-Operative Follow-up	2 weeks ± 3 days after implant surgery
Visit 5	Implant Uncovering	13 weeks ± 1 week after implant surgery
Visit 6	Restorative Records	3 weeks ± 1 week post-uncovering
Visit 7	Definitive Restoration (Loading)	4 - 6 months from implant insertion
Visit 8	3-month follow-up	3 months ± 2 weeks post-functional loading
Visit 9	6-month follow-up – Primary Endpoint	6 months ± 1 month post-functional loading
Visit 9.5	9-month follow-up	9 months ± 1 month post-functional loading
Visit 10	12-months follow-up	12 months ± 2 month post-functional loading
Visit 11	15-months follow-up	15 months ± 2 month post-functional loading
Visit 12	18-months follow-up	18 months ± 2 month post-functional loading
Visit 13	21-months follow-up	21 months ± 2 month post-functional loading
Visit 14	24-months follow-up	24 months ± 2 month post-functional loading

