5.5 Implant Uncovering (Visit 5)

At 13 weeks (± 1 week) following implant surgery, the implant will be uncovered, the short-term implant stabilization will be checked, a healing or standard abutment will be placed, and the soft tissue adapted around the abutment. Short-term implant stabilization will be tested by applying a clockwise torque of 35 Ncm to the implant. If the implant does not rotate with torque application, stabilization will be considered a success of the device and the event will be logged as a "success of short-term stabilization". Should the implant rotate with torque application, the abutment will be removed, and the implant will be left and allowed to heal for an additional month and re-evaluated for successful integration. Lack of stabilization will be considered a failure of the device and the event will be logged as a "failure of short-term stabilization". In particular, the subject will have the following procedures and/or evaluations performed and documented at this visit:

- Dental and medical history
- Concomitant medication
- Adverse event check
- Oral hygiene evaluation
- Uncover implant, place healing abutment
- Implant stability by clockwise torque with maximum of 35 Ncm to confirm stabilization
- Standardized periapical radiograph
- Intra-oral photographs

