5.16 Protocol Related Procedures

5.16.1 Early Withdrawal

Any subject may withdraw from the study at any time without prejudice and will be offered an alternative treatment for his/her dental condition. Subjects will be advised of the need for the prescribed follow-up visits for their ongoing care, well-being, and collection of any safety data.

The Investigator may withdraw any subject from the study in the case of:

- Non-compliance with the protocol
- Failure to attend the follow-up visits
- Serious Adverse Event (SAE) or adverse event, which in the opinion of the Investigator prevents

the subject's further participation in the study.

The subject withdrawal will be documented on a study termination form and must include the reason for the subject withdrawal. Efforts should be made to capture the primary study endpoint for each subject prior to withdrawal, if possible.

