5.16.3 Subject Replacement Policy

Subjects withdrawn from the study after enrollment will not be replaced.

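### A leaver's primary endpoint is measured at exit with no minimum loading time, so the text permits (but does not direct) an early firm implant to count as a six-month success

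*Combined protocol and SAP*

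**What the plan says.** The primary endpoint is a composite of implant success with a fixed final time point. In the Synopsis its last mobility component is "No construct mobility upon palpation at 6 months post- functional loading". Section 2.1 ties that component to a visit: "Continued stabilization is assessed at 6-months post-functional loading (Primary Follow-up, Visit 9) by applying manual palpation". Table 1 in Section 5.1 gives Visit 9 a window of "6 months ± 1 month post-functional loading".

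Two sections deal with subjects who leave before that. Section 7.4.4 (Missing Data) says "every effort will be made to measure their primary endpoint immediately prior to discontinuation if possible. No missing data will be imputed". Section 5.16.1 (Early Withdrawal) says "Efforts should be made to capture the primary study endpoint for each subject prior to withdrawal, if possible". Section 5.16.3 adds: "Subjects withdrawn from the study after enrollment will not be replaced".

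On timing, Section 3.11.1 says "Implant success will be assessed at post-functional loading follow-ups", and the first of these is Visit 8, at 3 months. Section 7.1 plans a descriptive summary of the primary endpoint without a test. Section 7.4 names mean, standard deviation and range. Neither gives a denominator, an interval, or a rule for an endpoint value obtained before the Visit 9 window.

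**The concern.** A subject covered by Section 7.4.4 has not completed the primary assessment, so the exit measurement will normally come before six months of loading. Both sections nevertheless call it the primary endpoint. A subject who leaves at month 1 or month 3 with a firm implant could then sit in the data set with a primary endpoint value of success, and nothing in the analysis section tells the programmer to keep it out of the six-month rate.

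Such an implant can still fail by month 6. Section 1 gives the third efficacy purpose as success after six months of loading while the material undergoes significant resorption, and Table 3 lists loss after restoration among the expected device effects. Counting early exits as successes can therefore leave the rate unchanged or raise it, but cannot lower it relative to the leavers' true six-month status.

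At stake is the reliability of a descriptive rate from 20 subjects that will inform a larger study. No test or success threshold depends on it. The issue is confined to successes recorded at exit after loading.

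**Working it through.** **Reading the text**

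1. The endpoint's last component is palpation at Visit 9. The window runs from 6 − 1 = 5 months to 6 + 1 = 7 months after loading (Synopsis, Section 2.1, Table 1).
2. The exit measurement is taken just before discontinuation, at whatever time that falls (Sections 7.4.4 and 5.16.1). No section applies the Visit 9 window to it.
3. The no-imputation sentence does not clearly settle the matter, because an exit measurement is observed and is given the endpoint's name.
4. Section 7.4.3 requires all enrolled subjects to be accounted for and early withdrawals to be summarised. It does not require their endpoint status to be shown apart from Visit 9 results.

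**Size**

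The plan gives no expected success rate or dropout rate, so there is no figure to reproduce and the counts below are assumptions. Inputs: N = 20 (Section 3.5), no replacement (Section 5.16.3), and all 20 assumed to receive TN-SM. Let f be the number of failures and k the number of early post-loading exits with a firm implant.

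- Exits counted as successes: (20 − f)/20
- Complete case (exits dropped): (20 − f − k)/(20 − k)
- Worst case (exits counted as failures): (20 − f − k)/20

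Results for f = 2, with Clopper-Pearson 95% intervals:

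| k | Exits as successes | Complete case | Worst case |
|---|---|---|---|
| 1 | 18/20 = 90.0% (68.3–98.8) | 17/19 = 89.5% (66.9–98.7) | 17/20 = 85.0% (62.1–96.8) |
| 2 | 18/20 = 90.0% (68.3–98.8) | 16/18 = 88.9% (65.3–98.6) | 16/20 = 80.0% (56.3–94.3) |
| 3 | 18/20 = 90.0% (68.3–98.8) | 15/17 = 88.2% (63.6–98.5) | 15/20 = 75.0% (50.9–91.3) |

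The gap between the first two rates is f/(20 − k) − f/20 = fk/[20(20 − k)]. In percentage points:

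| f | k = 1 | k = 2 | k = 3 |
|---|---|---|---|
| 0 | 0.0 | 0.0 | 0.0 |
| 1 | 0.3 | 0.6 | 0.9 |
| 2 | 0.5 | 1.1 | 1.8 |
| 4 | 1.1 | 2.2 | 3.5 |

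The gap between exits as successes and worst case is k/20, or 5 points per exit whatever f is: 5 to 15 points for 1 to 3 exits. For scale, the exact interval for 18/20 is 98.8 − 68.3 = 30.5 points wide.

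The expected overstatement is smaller than that bound. If an implant firm at exit would fail by month 6 with probability p, the rate is overstated on average by kp/20. Assuming p between 0 and 20%, that is 0 to 1 point per exit.

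**The case against.** The strongest reply is that the endpoint definition already answers the question. An implant palpated at month 1 has no six-month palpation, so the composite is not met, and the Synopsis places the primary analysis after six months of loading. On this view Sections 7.4.4 and 5.16.1 are about data collection: they ask sites for a last assessment and do not tell the analyst to pool it. Using a month-1 value as the month-6 value is also arguably a form of imputation, which Section 7.4.4 rules out.

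Much of this stands. The definition favours the safe reading. A reader might infer that the plan instructs the analyst to carry early exits forward as successes; no sentence says so. What remains is that both sections give the early measurement the endpoint's name, and none says that it cannot count as a success at six months.

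The size is also fairly challenged. A reader might take 5 points per exit as the bias, but it would be that large only if every firm leaver went on to fail. Complete case is not an unbiased reference either: if early failures are kept, early leavers can enter it only as failures, which can pull it down. In the f = 2 example, if all the firm leavers stayed firm, complete case would be 0.5 to 1.8 points too low.

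Finally, Section 7.4.3 makes early exits visible, and Sections 5.16.4 and 7.4.2 have deviations from visit windows recorded and summarised. That helps a reader count leavers but does not classify their endpoint.

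**Conclusion.** The point holds as a modest, inexpensive improvement. The text permits, without directing, an implant that is firm at an early post-loading exit to enter the six-month success rate. For 0 to 4 failures and 1 to 3 such exits, all assumed, the rate would be 0 to 3.5 points above complete case, well inside the sampling uncertainty of 20 subjects. The worst-case bound, 5 points lower per exit, shows how much is unknown.

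The documents do not support a claim that the trial's conclusion would be wrong: the study is a descriptive pilot with no hypothesis test or success threshold. Nor does the point extend to exits before loading, because Section 3.11.1 places the assessment of implant success at post-loading visits.

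**What to change.** In Sections 7.1 and 7.4.4, state that:

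1. An exit assessment before the Visit 9 window opens (5 months after loading) can record a protocol-defined failure but cannot establish six-month success.
2. Subjects with no failure and no Visit 9 result are classed as status unknown, and their number is reported separately.
3. The six-month success rate among all enrolled subjects who received TN-SM is reported twice, with unknowns counted as successes and as failures, each with an exact 95% CI. The upper figure equals the rate obtained by counting firm exits as successes whenever those exits are the only unknowns. The difference is that it is labelled as a bound and shown beside the lower one.
4. If a rate among subjects of known status is also shown, a note says that it can be biased downward.

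The cost is a few lines of wording and two rates with intervals, with no new data. The rate may look slightly less favourable, and the range will look wide for 20 subjects.

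A separate point, unrelated to withdrawal, can be settled in the same amendment. If the implant rotates at the 13-week torque test, Section 5.5 says "the implant will be left and allowed to heal for an additional month and re-evaluated for successful integration", whereas the composite in the Synopsis requires no rotation at 13 weeks. The two passages must be reconciled on whether the first rotation is a primary-endpoint failure.

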9.1 Regulatory and Ethical Requirements

9.1.1 Informed Consent

Informed consent will be obtained from all subjects prior to study participation as described in Section 5.2.1.

9.1.2 Institutional Review Board

Prior to initiation of any study procedures, the protocol and informed consent will be submitted to an IRB for review and approval. In addition, any amendments to the protocol or informed consent will be reviewed and approved (if necessary) by the IRB. The sponsor must receive a letter documenting the IRB approval at the center prior to the initiation of the study at the center.

The investigator is responsible for providing the appropriate reports to the IRB during the course of the clinical study. This will include the following:

- Informing the IRB of the study progress periodically as required, but at a minimum annually
- Reporting any unanticipated serious adverse device effects within 10 working days of becoming aware of the event
- Reporting any deviations from the protocol that adversely affect the risk/benefit ratio, the rights, safety, or welfare of the participants, or integrity of the study
- Providing any other reports requested by the IRB

9.2 Reports and Record Management

9.2.1 Investigator Records

The following will be required from the investigator prior to the initiation of the study:

- A signed confidentiality agreement
- Signed and dated curriculum vitae of the investigator(s) and a copy of his/her dental license
- Signed financial disclosure

- A signed copy of the final protocol and any amendments
- A signed copy of the clinical study agreement with the sponsor
- IRB approval letter and IRB approved informed consent document

9.2.2 Case Report Forms

The investigator will be responsible for the accuracy of the data entered on the Electronic Case Report Forms (eCRFs). The investigator will also allow a RevBio representative and/or regulatory bodies to review the data reported on the case report form with the source documents as far as is permitted by local regulations.

9.2.3 Source Documents

Source documents are defined as the original point of entry of a specific data point. Source documents will include, but are not limited to, progress notes, electronic data, computer printouts, radiographs, and recorded data from automated instruments. All source documents pertaining to this study will be maintained by the investigator and made available for inspection by authorized persons.

